In addition, duration of exposure during the 12-week Treatment Period will be summarized with descriptive statistics (number of non-missing observations, mean, standard deviation, median, minimum and maximum duration and total subject-years) and by total subject-years. Total subject-years of OMT, LCIG and PEG-J exposure will be calculated by summing the duration of exposure across the respective set of subjects and dividing this sum by 365.25 (1 year will be considered to be 365.25 days).

During the Transition Period

The duration of study drug exposure for LCIG subjects during the Transition Period will be summarized with descriptive statistics (number of subjects with non-missing data, mean, standard deviation, median, minimum and maximum). The duration of LCIG study drug exposure will be calculated for each subject as the date of the last infusion of LCIG study drug during the Transition Period minus the date of the last infusion of LCIG study drug during the 12-week Treatment Period.

The duration of PEG-J exposure for LCIG subjects during the Transition Period will be summarized with descriptive statistics (number of subjects with non-missing data, mean, standard deviation, median, minimum and maximum). For subjects with a PEG-J tube removal after their last infusion of LCIG study drug during the Transition Period, the duration of PEG-J exposure for each subject will be calculated as the date of their final PEG-J removal minus the date of their last infusion of LCIG study drug during the 12-week Treatment Period. For subjects without a PEG-J tube removal after their last infusion of LCIG study drug during the Transition Period, the duration of PEG-J exposure for each subject will be calculated as the date of their final participation in Study M15-535 (last contact or visit date) minus the date of their last infusion of LCIG study drug during the 12-week Treatment Period

Overall

The overall duration of study drug exposure for LCIG subjects and the overall duration of study participation for OMT subjects will be summarized with descriptive statistics (number of subjects with non-missing data, mean, standard deviation, median, minimum

and maximum). The overall duration of LCIG study drug exposure will be calculated for each subject as the date of the last infusion of LCIG study drug minus the date of the first infusion of LCIG study drug plus 1. The overall duration of study participation for OMT subjects will be calculated for each subject as the date of the last visit minus the date of randomization.

The overall duration of PEG-J exposure for LCIG subjects will be summarized with descriptive statistics (number of subjects with non-missing data, mean, standard deviation, median, minimum and maximum). The overall duration of PEG-J exposure for each subject will be calculated as the date of their final PEG-J removal or the date of their final participation in Study M15-535 (last contact or visit date) if there is no PEG-J removal minus the date of their initial PEG-J placement + 1.

8.2 **Duration of NJ Period**

Duration of NJ Period for each subject who undergoes the optional NJ period will be calculated as the date of NJ removal minus the first NJ infusion date + 1. The first NJ infusion date will be recorded on the Study Drug Administration eCRF. The number and percentage of subjects with each specific number of days will be summarized. In addition, the duration of NJ Period in days will be summarized with descriptive statistics (number of non-missing observations, mean, standard deviation, median, minimum and maximum duration).

8.3 LCIG Daily Prescribed Dose

Each subject's LCIG dose will be individually titrated by adjustment of the LCIG pump settings for the morning dose (mL), continuous flow rate (mL/hr) and extra dose amount (mL). The initial LCIG pump settings and the LCIG pump settings at the conclusion of each clinic visit will be recorded on the Study Drug Prescription eCRF. Subjects are to administer LCIG over a full 16-hour period each day beginning with a morning dose. Extra doses are to be administered only if needed. The daily prescribed dose will be calculated as the morning dose plus 16 times the continuous flow rate. The daily

prescribed dose will be summarized in milligrams (mg) of levodopa using the conversion factor of 1 mL LCIG = 20 mg levodopa.

The daily prescribed dose will be summarized with descriptive statistics (number of subjects with non-missing observations, mean, standard deviation, median, minimum and maximum values) for the following.

- Initial LCIG prescription
- First optimized prescription following PEG-J placement
- Final prescription

Descriptive statistics will also be presented for the change in the daily prescribed dose from initial LCIG prescription to first optimized prescription following PEG-J placement and to final prescription and from first optimized prescription to final prescription.

8.4 **Total Daily Levodopa Dose**

For all randomized subjects, the total daily levodopa dose on the day prior to Visit 1 and on the day of randomization will be considered the subject's screening and baseline levodopa dose, respectively. Following Screening Visit 3, subjects randomized to the LCIG group will have NJ/PEG-J placement and discontinue all anti-PD medications other than levodopa-carbidopa that will be continued during LCIG treatment as post-infusion nighttime therapy. Subjects in the LCIG group are to record all LCIG infusions during the 3 days before each scheduled study visit on a Subject Dosing Diary. Subjects in the OMT group are to record all anti-parkinsonian medications taken on the Subject Dosing Diary.

For each Subject Dosing Diary, the overall total daily dose of levodopa will be determined for each subject in the Safety Dataset, as well as the total for each dosing source for each subject in the LCIG group: LCIG morning dose, LCIG continuous infusion, LCIG extra dose, and LCIG overall. Each subject's average daily dose at each visit, overall and by dosing source, will be calculated by summing the total dose on each Subject Dosing Diary assigned to the visit and dividing by the number of diaries recorded. For LCIG subjects,

only diaries reporting at least 12.8 hours of pump operation and only diaries after the initial LCIG titration will be included in this calculation.

For each scheduled visit the mean daily levodopa dose will be summarized, overall and by dosing source, with descriptive statistics (number of subjects with observations, mean, standard deviation, median, minimum and maximum values). The summaries for LCIG extra dose should only include the subjects who dosed in this manner at the visit.

8.5 **Daily Treatment Duration**

The LCIG pump start time and end time at each clinic visit will be recorded on the Dosing Diary eCRF. Daily treatment duration (hours of pump operation) will be summarized with descriptive statistics (mean, standard deviation, median, minimum and maximum duration) at each visit.

8.6 **Tube Replacements**

The number and percentage of LCIG subjects with each specific count of PEG-J tube replacements will be summarized as well as the number and percentage of LCIG subjects with one or more replacements. The number of PEG-J tube replacements will also be summarized by descriptive statistics. The time to the first PEG-J tube replacement will also be estimated using Kaplan-Meier methodology. For the Kaplan-Meier analysis, subjects who did not have a PEG-J tube replacement during the study will be censored at the end of their Study M15-535 PEG-J tube exposure. Subjects with a PEG-J tube removal after their last infusion of Study M15-535 study drug will be censored at this final tube removal date. Subjects without a PEG-J tube removal after their last infusion of Study M15-535 study drug will be censored on the date of their final participation in Study M15-535 (last contact or visit date).

8.7 **Duration of Initial LCIG Titration**

Duration of initial LCIG titration for each subject will be calculated as the date of the first optimized prescription minus the first LCIG infusion date + 1. The first LCIG infusion date will be recorded on the Study Drug Administration eCRF. The current

LCIG pump settings at the conclusion of each clinic visit will be recorded on the Study Drug Prescription eCRF. The first set of pump settings that remains unchanged for at least 7 days will be considered the first optimized prescription. The number and percentage of subjects with each specific number of titration days will be summarized. In addition, the duration of initial titration in days will be summarized with descriptive statistics (number of non-missing observations, mean, standard deviation, median, minimum and maximum duration).

9.0 Efficacy and Health Outcome Analysis

9.1 **General Considerations**

This is a randomized open-label study. Unless otherwise specified, statistical tests will be two-sided and the null hypothesis will be rejected at the significance level of $\alpha = 0.050$. *P* values will be rounded to 3 decimal places before assessing statistical significance. Unless noted otherwise, all analyses will be performed with the Intent-to-Treat Dataset. Missing data will not be imputed unless otherwise specified.

9.2 **Primary Efficacy Analysis**

UDysRS Total Score

The UDysRS was developed to evaluate dyskinesia in Parkinson's disease. It contains two primary sections with 26 questions:

Historical [Part 1 (On-Dyskinesia) and Part 2 (Off-Dystonia)]

Objective [Part 3 (Impairment) and Part 4 (Disability)]

Part 1 contains 11 questions about the on time dyskinesia and the impact of on-dyskinesia on experiences of daily living. Part 2 contains 4 questions of off-dystonia rating. Part 3 contains 7 questions about objective evaluation of dyskinesia impairment and Part 4 contains 4 questions regarding dyskinesia disability. Each question is scored with respect to severity, which is rated on a scale where 0 = normal, 1 = slight, 2 = mild, 3 = moderate

and 4 = severe. The UDysRS total score is obtained by summing the item scores, ranging from 0 to 104.

The primary efficacy variables will be the change from baseline to Week 12 in the UDysRS total scores. It will be estimated using PROC MIXED and a mixed-effect model repeated measures (MMRM) for the change from baseline to each scheduled post-baseline visit. The model will include fixed, categorical effects for treatment, country, visit, and treatment-by-visit interaction, with continuous fixed covariates for baseline score and the baseline score-by-visit interaction. The unstructured covariance structure will be used to estimate the within subject variance-covariance structure and Satterthwaite's approximation will be used to estimate the denominator degrees of freedom. If the model fails to converge, the first order autoregressive (AR[1]) covariance structure will be substituted. If the model still fails to converge, the compound symmetry (CS) covariance structure will be substituted. Type III sum-of-squares and least-square (LS) means will be used for statistical evaluations. The LS mean and 95% confidence interval obtained from the model will be presented. The primary comparison will be the contrast between LCIG and optimized medical treatment at the Week 12 Visit. The primary null and alternative hypotheses may be expressed as:

> H₀: $\mu_{LCIG} = \mu_{OMT}$ H_A: $\mu_{LCIG} \neq \mu_{OMT}$

Where μ_{LCIG} is the mean change from baseline to Week 12 for LCIG group in the UDysRS total score and μ_{OMT} is the mean change from baseline to Week 12 for OMT group in the UDysRS total score. The statistical tests at other visits will be considered secondary.

The change in the UDysRS total score to each planned visit and to the final visit will also be summarized by the following descriptive statistics: number of non-missing observations, mean baseline score and standard deviation, mean visit score and standard deviation, median visit score and range, mean change from baseline and its standard

deviation and standard error, median change from baseline and range. The hypothesis of change from baseline will be evaluated at each visit with a one-sample t-test.

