4.2 Design Diagram

This is a Phase 3b, open-label, randomized multicenter 12 week study assessing the efficacy of LCIG treatment compared to OMT on dyskinesia in subjects with Advanced Parkinson's Disease.

The study will consist of three sequential parts:

Part 1: Screening period. The screening period will consist of three visits, Visit 1 (V1), Visit 2 ([V2] [optional]) and the Randomization Visit (V3) in which the subject will be

assessed to determine eligibility. The duration of the Screening Period will be between 30-67 days to accommodate the required procedures, training and collection of diaries, and to allow for stabilization of anti-PD medications and medications to treat dyskinesia. All anti-PD medications and medications to treat dyskinesia are required to be stable for a minimum of 30 days prior to randomization.

Part 2: Treatment period. Those subjects randomized to OMT at the end of V3 will remain on their current optimized anti-PD regimen. The day after randomization will be considered Day 1 of their treatment period and subjects will have study visits at the end of Weeks 2, 4, 8, and 12. Subjects randomized to LCIG treatment must discontinue all other anti-PD medications other than amantadine (e.g., dopamine agonists, COMT-inhibitors, MAO-B inhibitors, anti-cholinergics, and subcutaneous apomorphine, etc.) prior to LCIG treatment initiation on Day 1 (V4); these medications should be tapered off within 14 days after randomization according to the discretion of the Investigator. With the exception of apomorphine, levodopa containing formulations or amantadine, these medications may be restarted if indicated by the subject's individual condition, but not within the first 28 days after LCIG treatment initiation. Optional nasojujunal (NJ) and/or percutaneous endoscopic gastrostomy with a jejunal tube (PEG-J) placement will then be placed. After that, the subject may begin initiation and titration of LCIG infusion to be adjusted to obtain the optimal clinical response in 14 days. The day of initial NJ or PEG-J placement will be considered Day 1 for subjects in the LCIG group. Study visits happen at the end of Weeks 2, 4, 8, and 12.

Characterization Carbidopa Intestinal Gel (LCIG) M15-535 - Statistical Analysis Plan Version 1.0 - 21 May 2018

[figure not shown]

Figure 1. **Study Design Schematic**

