4.3 Sample Size

Approximately 60 subjects will be enrolled into the study and randomized in a 1:1 ratio to either optimized medical treatment (OMT) or LCIG treatment. Subject randomization will be stratified by country. For sample size determination, it is assumed that the difference of improvement is 10 points on UDysRS total score between the LCIG treatment group and OMT group based on results reported by Pahwa et al (2015). The pooled standard deviation is assumed to be 12 based on results reported by Goetz et al (2013). Assuming that the treatment group difference is 10 points and the pooled standard deviation is 12, 27 subjects per group will have 85% power to declare statistical significance on the primary endpoint at a two-sided significance level of 0.050 based on calculations using nQuery + nTerim 4.0. It is further assumed that 10% of randomized subjects in either treatment group will not provide post-randomization efficacy assessment. Therefore the total planned enrollment is decided to be approximately 60 subjects.

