9.3 Additional Efficacy Analyses

Secondary Analysis of the Primary Efficacy Variables

Analysis of covariance (ANCOVA) analyses will be carried out on change from baseline to final UDysRS total score. The ANCOVA model will contain treatment and country as the main effects and baseline score as the covariate. Sensitivity analyses will be carried out on the above variables with the same ANCOVA model using all randomized subjects. In this analysis, Baseline Observation Carried Forward (BOCF) will be applied to subjects who do not have post-randomization assessment of UDysRS.

Analysis of Secondary Efficacy Variables

The MMRM model and the descriptive statistic summary described for the UDysRS total score will also be used to evaluate the change from baseline to Week 12 in each of the following efficacy endpoints (with the exception of the CGI-C, which the score itself shows the changes):

- "ON" time without troublesome dyskinesia as measured by the PD Diary
- Parkinson's Disease Questionaire-8 (PDQ-8) summary index
- Clinical Global Impression of Change (CGI-C) Score
- UPDRS Part II Score
- "OFF" time as measured by the PD Diary
- **UPDRS** Part III Score

PD Diary variables will be normalized to a 16 hour awake time and the time recorded by the subject on the 3 diaries completed prior to each visit will be averaged.

For CGI-C, an ANCOVA model containing treatment and country as the main effects and baseline CGI-S as covariate will be carried out.

"ON" time without troublesome dyskinesia as measured by the PD Diary, PDQ-8 summary index, CGI-C score, UPDRS Part II and Part III score, and "OFF" time as measured by the PD Diary are key secondary endpoints. If the primary efficacy variable is statistically significant, each of the secondary variables will be tested using the fixed sequence above as a gatekeeping procedure and at α level of 0.050. Testing will cease at the point that a secondary variable fails to demonstrate statistical significance.

All secondary efficacy variables will be summarized by the number of subjects with nonmissing data, mean, standard deviation, median, minimum and maximum.

Analysis of Additional Efficacy and Health Variables

Efficacy will also be assessed using the following additional measures:

- UDysRS Historical Score, Objective Score and Parts 1 through 4 Scores
- "ON" time with troublesome dyskinesia and "ON" time without dyskinesia as measured by the PD Diary
- mAIMS

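### Cheap improvement: use Kenward-Roger instead of Satterthwaite in the primary MMRM, because the implied model-based standard error is slightly too small when Week 12 data are missing

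*SAP*

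**What the plan says.** SAP 9.2 estimates the change in UDysRS total score with PROC MIXED. The fixed effects are treatment, country, visit, treatment-by-visit, baseline and baseline-by-visit. The within-subject covariance is unstructured, and Satterthwaite's "approximation will be used to estimate the denominator degrees of freedom". If the model does not converge, AR(1) is substituted, then compound symmetry. The primary comparison is the treatment contrast at Week 12. The SAP does not say how the standard error is computed and names neither Kenward-Roger nor an empirical (sandwich) variance. Protocol 8.1.3.1 gives the same model terms but no covariance structure or degrees-of-freedom method.

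SAP 9.3 extends the model to the secondary variables: "The MMRM model and the descriptive statistic summary described for the UDysRS total score will also be used". CGI-C is excepted and has an ANCOVA. Additional continuous endpoints use the same MMRM.

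On size, SAP 4.3 states that "27 subjects per group will have 85% power", assuming that "the treatment group difference is 10 points and the pooled standard deviation is 12". It also assumes that "10% of randomized subjects in either treatment group will not provide post-randomization efficacy assessment". On visits, SAP 4.2 states: "Study visits happen at the end of Weeks 2, 4, 8, and 12".

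**The concern.** The Satterthwaite method adjusts only the degrees of freedom. The standard error is still computed as if the estimated covariance matrix were the true one. With an unstructured covariance, a small sample and missing data, that standard error is biased low. Kenward-Roger adds a correction to the variance. For a single contrast under an unstructured covariance it gives the same degrees of freedom, so only the standard error differs.

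At stake are the primary test at two-sided 0.050 and the interval reported with it. Incomplete follow-up is realistic under this plan:

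- The 10% loss in SAP 4.3 covers only subjects with no post-randomization assessment. Later dropout among the remaining 54 is not budgeted.
- One missing item out of 26 voids the UDysRS total (SAP 9.4, Table 1).
- The Week 12 window opens at Day 71, and LCIG assessments more than 1 day after the last infusion are not used (SAP 6.5). A subject who terminates before Day 71 therefore has no Week 12 value.

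**Working it through.** **1. The plan's own figure.** Difference 10, SD 12, 27 per group, two-sided 0.050 (SAP 4.3). Noncentrality = 10 / (12 × √(2/27)) = 3.06 with 52 degrees of freedom, giving power of 85.2% by the two-sample t-test. The stated 85% is reproduced. Enrolment: 27 / 0.9 = 30 per group, 60 in total, and 60 × 0.9 = 54 evaluable. The figure 54 is derived; the documents do not state it.

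**2. Parameters to estimate.** Four visits give 4 × 5 / 2 = 10 covariance parameters. Fixed effects with 7 countries (Protocol 5.1 plans about 6 to 8): intercept 1 + treatment 1 + country 6 + visit 3 + treatment-by-visit 3 + baseline 1 + baseline-by-visit 3 = 18.

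**3. The two standard errors.** Let l pick out the Week 12 contrast, and let Φ = (Σ Xᵢ′ Vᵢ⁻¹ Xᵢ)⁻¹ be evaluated at the estimated covariance. The model-based SE is √(l′Φl). Kenward-Roger replaces Φ by Φ plus a correction for the estimation of V.

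**4. Simulation at 27 per arm, 30,000 null trials per scenario.** The Monte Carlo SE of a type I error rate is √(0.05 × 0.95 / 30,000) = 0.13 points.

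| Missing data | SE short relative to Kenward-Roger | Type I error, Satterthwaite | Type I error, Kenward-Roger |
|---|---|---|---|
| None | about 0% | 4.94% | 4.93% |
| 15% dropout | about 0.5% | 5.36% | 5.24% |
| 20% dropout + 5% intermittent | about 1% | 5.23% | 4.99% |
| 30% dropout + 5% intermittent | about 1.7% | 5.52% | 5.16% |

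The Satterthwaite excess over 5% in the three missing-data rows is 0.36 / 0.13 = 2.8, 0.23 / 0.13 = 1.8 and 0.52 / 0.13 = 4.0 Monte Carlo SEs.

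The root-mean-square Kenward-Roger SE was closer to the true SD of the estimate in each missing-data scenario. In one of them it was 3.685, against 3.648 for Satterthwaite and a true SD of 3.699. The ratio is 3.685 / 3.648 = 1.010. The shortfall from the true SD falls from 0.051 to 0.014.

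**5. Interval width and power at 54 subjects, about 8,000 trials per scenario.** Assumptions: SD 12 at every visit, 7 countries, correlation 0.6 unless stated, true difference 10.

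| Missing data | Kenward-Roger SE larger by | 95% half-width, Satterthwaite / Kenward-Roger | Power, Satterthwaite / Kenward-Roger |
|---|---|---|---|
| None | 0.05% | 6.631 / 6.635 | 84.39% / 84.38% |
| 10% dropout | 0.36% | 6.867 / 6.892 | 81.35% / 81.14% |
| 20% + 5% intermittent | 0.78% | 7.162 / 7.218 | 77.94% / 77.52% |
| 20% + 5% intermittent, correlation 0.8, AR(1) | 0.72% | 7.163 / 7.215 | 78.01% / 77.69% |
| 20% + 5% intermittent, correlation 0.3 | 1.12% | 7.439 / 7.522 | 74.55% / 73.92% |

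The largest change in half-width is 7.522 − 7.439 = 0.083 UDysRS points. The largest loss of power is 74.55 − 73.92 = 0.63 points.

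**6. When the conclusion would change.** The degrees of freedom are equal, so the decision differs only if |t| under Satterthwaite lies between the critical value and that value times the SE ratio, at most about 1.017 here.

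**The case against.** The strongest reply is that nothing in the plan is wrong. An unstructured covariance with Satterthwaite degrees of freedom is a recognised, fully prespecified choice and contradicts nothing in the protocol. That stands, and it is why this is only an improvement.

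A reader might infer that the primary test clearly breaches 0.050 at the planned size, or that the SAP prescribes an uncorrected standard error. Neither is supported. The SAP is silent on the standard error, so the model-based form is an inference. The 8,000-trial runs at 54 subjects gave Satterthwaite type I error of 4.73% to 5.21%, within their simulation error of 5% (Monte Carlo SE 0.24 points). A separate 6,000-trial run at 15% dropout gave 5.35%, which is only 0.35 / 0.28 = 1.2 Monte Carlo SEs above 5%. An excess shows only in the larger runs with missing data, and it is small.

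A comparison of a mean SE with the true SD would overstate the shortfall, since a mean SE falls below the true SD even when the variance estimate is unbiased. That does not affect the root-mean-square comparison above.

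Three further limits stand. The 30% dropout scenario is a stress case, since SAP 4.3 gives no rate for later dropout. Kenward-Roger reduces the bias but need not remove all of it (5.24% at 15% dropout). The secondary variables were not simulated, so it cannot be said that they too exceed 0.050. PDQ-8, for example, has only Weeks 8 and 12 (SAP 6.5), hence 2 × 3 / 2 = 3 covariance parameters rather than 10.

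**Conclusion.** The point holds as a cheap improvement. With complete data the two methods agree. With missing Week 12 data the implied standard error at 54 evaluable subjects is short relative to Kenward-Roger by about 0.5% to 1.7% over 15% to 30% dropout, the two heavier scenarios including 5% intermittent missing data. Type I error is at most about 5.2% to 5.5%. The primary conclusion would change only in a near-tie.

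These sizes rest on assumed dropout, within-subject correlation and visit SDs, none of which the documents give. The 8,000-trial runs used the expected information; software using the observed information may differ slightly.

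**What to change.** In SAP 9.2, replace Satterthwaite with Kenward-Roger (ddfm=kr in PROC MIXED) for the primary MMRM. Carry the same option through SAP 9.3 to every endpoint that uses this model. State the degrees-of-freedom method for the AR(1) and compound symmetry fallbacks as well; a change worded for the unstructured model alone would leave them undefined. The equal degrees of freedom and the figures above apply to the unstructured model only.

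The cost is one option in the SAP and the program. The protocol names no degrees-of-freedom method, so its text need not change. Intervals widen by about 0% to 1.7%. Power falls by about 0 to 0.6 points at 54 subjects with up to 20% dropout, so the change is nearly but not exactly free.

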5.5.5 Blinding

This is an open-label study with randomized treatment assignment. All eligible subjects will be randomized in a 1:1 ratio through the IRT system to receive OMT or LCIG treatment in an open-label manner. Site personnel will be blinded to the randomization schedule.

Central blinded raters will be used to rate Parts 3 and 4 of the UDysRS, the primary efficacy endpoint for this study. Assessment obtained at V3 will serve as the baseline for clinical assessment. The scales will also be performed at Weeks 2, 4, 8, and 12. The scoring for Parts 3 and 4 are to be performed by a trained central blinded rater who will not have access to the results of other study assessments or medical records for the subject and who will not participate in the care or management of the subject. Each rating is based on the video recording of the subject.

5.5.6 **Treatment Compliance**

The Investigator or his/her designated and qualified representatives will administer/dispense LCIG study drug only to subjects enrolled in the study and randomized to LCIG treatment in accordance with the protocol. The study drug must not be used for reasons other than that described in the protocol. The site will review LCIG cassette usage at drug resupply visits and assess compliance at each visit.

5.5.7 **Drug Accountability**

Initial study supplies and 6 weeks of LCIG cassettes will be supplied to the Investigator by the drug depot. It is at the discretion of AbbVie and/or the Investigator to discontinue subjects from the study who fail to take and/or return the appropriate amount of study drug.

Treatment regimen compliance will be also be assessed by the Subject Dosing Diary.

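### If the unstructured MMRM fails to converge, SAP 9.2 falls back to structures with one variance for all visits, so the Week 12 standard error may be wrong if variability differs by visit

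*SAP*

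**What the plan says.** SAP 9.2 models change from baseline in UDysRS total score at each scheduled visit in PROC MIXED. It uses an unstructured within-subject covariance and Satterthwaite degrees of freedom, and the primary comparison is LCIG against OMT at Week 12. The fallback has two steps:

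- "If the model fails to converge, the first order autoregressive (AR[1]) covariance structure will be substituted"
- if that fails too, "the compound symmetry (CS) covariance structure will be substituted"

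SAP 9.2 names no structure with a separate variance per visit, no time-based structure and no empirical (sandwich) standard error. Protocol 8.1.3.1 gives the same fixed effects but no covariance structure, so the SAP is the only place where this is settled.

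On the schedule, SAP 4.2 says "Study visits happen at the end of Weeks 2, 4, 8, and 12", and Protocol 5.5.5 agrees for the primary scale: "The scales will also be performed at Weeks 2, 4, 8, and 12". On variability, the only figure is the planning value in SAP 4.3: "Assuming that the treatment group difference is 10 points and the pooled standard deviation is 12, 27 subjects per group will have 85% power". Neither document gives an SD or a correlation by visit.

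**The concern.** AR(1) and CS as named estimate one residual variance from all four visits together. The primary contrast concerns one visit. Under either fallback its standard error would be built from an average of the Week 2, 4, 8 and 12 variances instead of the Week 12 variance, with nothing to correct a mismatch.

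Unequal variances are plausible here, because the visits capture different treatment states. Protocol 5.1.2.2 requires the Week 2 assessments even if LCIG titration is still going on, the synopsis allows dose adjustment up to Day 28, and SAP 6.5 gives Week 2 a window of Study Days 2 to 21.

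At stake is the error rate of the primary test, and through it entry to the fixed secondary sequence (SAP 9.5). A numerical failure in one program should not be able to move a nominal 5% test.

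**Working it through.** **Inputs from the documents.** Two-sided test "at a two-sided significance level of 0.050"; difference 10, SD 12 and 27 per group (SAP 4.3); subjects "randomized in a 1:1 ratio"; loss assumption that "10% of randomized subjects in either treatment group will not provide post-randomization efficacy assessment"; four post-baseline visits with gaps of 2, 4 and 4 weeks.

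**Input that must be assumed.** SDs at Weeks 2, 4 and 8. The Week 12 SD is held at the planned 12.

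**Step 1: the plan's own figure.** A two-sample t-test (noncentral t) with difference 10 and SD 12 gives 85.2% power at 27 per group and 83.8% at 26. Then 54/0.90 = 60. The stated sample size reproduces and is not affected by this point.

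**Step 2: parameter counts for four visits.** Unstructured has 10. AR(1) and CS have 2 (one variance, one correlation). Heterogeneous AR(1) or CS has 4 + 1 = 5, and heterogeneous Toeplitz 4 + 3 = 7. The present ladder drops straight from 10 to 2.

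**Step 3: large-sample ratio.** Under one common variance, the reported Week 12 standard error relative to the true one is

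r = sqrt(mean of the four visit variances) / SD at Week 12.

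This is exact for CS with complete data. Fitting AR(1) by likelihood to the same covariance matrices gives values within 0.01. The two-sided error is 2 × (1 − Φ(1.96 r)).

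For SDs 9, 10, 11, 12: (81 + 100 + 121 + 144)/4 = 111.5; sqrt = 10.56; r = 10.56/12 = 0.88. The true standard error with 27 per arm is 12 × sqrt(2/27) = 3.27. The fallback would report 0.88 × 3.27, about 2.87.

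**Step 4: simulation.** REML fits with 27 per arm, four visits, about 10% monotone dropout completely at random, treatment-by-visit and baseline-by-visit terms, country omitted, Satterthwaite df. There were 1,000 runs per scenario under each of three true correlation shapes, two of them tied to the real week spacing.

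| Assumed SDs, Weeks 2/4/8/12 | r | Error, large sample | r, simulated | Error, simulated |
|---|---|---|---|---|
| 12/12/12/12 | 1.00 | 5.0% | 0.99–1.02 | 4.9–5.3% |
| 10/10.5/11/12 | 0.91 | 7.5% | 0.88–0.91 | 7.1–8.0% |
| 9/10/11/12 | 0.88 | 8.5% | 0.86–0.91 | 7.6–9.1% |
| 7/9/11/12 | 0.83 | 10.5% | 0.81–0.84 | 9.1–11.2% |
| 15/14/13/12 | 1.13 | 2.7% | 1.08–1.13 | 2.5–3.4% |

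Simulated ranges cover AR(1) and CS together. Median df were 94 to 129, against 49 for the unstructured fit, so the critical value is slightly lower too.

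**Step 5: does a separate variance per visit cure it?** On 9/10/11/12 data (300 runs), the unstructured fit gave r = 0.998 and error 5.7% (simulation error about 1.3 points). AR(1) and CS on the same data gave 0.875 and 8.3%. In a second simulation (complete data, country omitted, 600 runs per scenario) the homogeneous fallbacks gave about 8 to 10% for 9/10/11/12 and 2 to 3% for 15/14/13/12. Heterogeneous AR(1) and CS stayed at about 4 to 6.5% in every scenario.

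**Step 6: visit spacing.** With equal SDs and correlations that follow the real weeks, AR(1) gave r between 0.998 and 1.001. With little missing data, the Week 12 contrast depends on the Week 12 variance and hardly on the modelled correlations.

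**The case against.** **It is a contingency.** The fallback is used only if the unstructured fit fails. In a separate check, 200 simulated trials (27 per arm, about 15% dropout, country omitted, a general optimiser and not PROC MIXED) gave no failure. If failure had an assumed 1% probability unrelated to the result, even the worst simulated error gives 0.99 × 5% + 0.01 × 11.2% = 5.06% overall; at 5% it is 0.95 × 5% + 0.05 × 11.2% = 5.31%. This stands, and it is why the point is only a cheap improvement.

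**The premise is not in the documents.** A reader might infer that the Week 12 intervals would be too narrow because change scores spread out over time. The documents do not support a direction. Titration still under way could make Week 2 more variable, and the synopsis expects titration to end within 7 days (direct PEG-J) or 14 days (with NJ), with extra days at discretion. A reader might also infer that the fallbacks are wrong in themselves, or that AR(1) fails because the visits are unevenly spaced. The first row of the table and step 6 show neither.

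**There is already a check.** The ANCOVA on change to final visit (SAP 9.3) does not use this covariance and could expose a discrepant standard error. It is supportive only and does not decide the primary test.

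**Sandwich errors are no free cure.** With 54 subjects, 7 countries, complete data, an AR(1) fit and 1,500 runs, uncorrected sandwich standard errors were 7 to 9% too small. With flat SDs the error rose from 5.5% (model-based) to 6.9%; with 14/13/12/12, from 4.3% to 7.9%. They helped only for steeply rising SDs (8/10/12/13: 11.0% to 7.3%). This stands, so a blanket sandwich requirement is not recommended.

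**Conclusion.** The point holds as a conditional one. If the unstructured fit fails and the residual variance at Week 12 differs from the average over visits, the fallback misstates the Week 12 standard error. Over the assumed SDs this runs from about 17% too small (error near 11%) to about 13% too large (error 2 to 3%, which costs power). With equal variances there is no error. These figures rest on assumed visit SDs, a Week 12 SD of 12, about 27 per arm and models without country. The documents fix neither the size nor the direction, and the trigger should be uncommon with four visits. The ladder is worth correcting because the repair is specific and nearly free, not because the primary result is likely to be affected.

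**What to change.** In SAP 9.2, replace the fallback with this order:

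1. Refit the unstructured matrix in Cholesky form (TYPE=FA0 of order equal to the number of post-baseline visits, so FA0(4) for UDysRS), with supplied starting values.
2. Heterogeneous Toeplitz.
3. Heterogeneous AR(1) or CS; state which comes first.
4. Homogeneous AR(1) or CS only as a last resort.

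Keep Satterthwaite df. Do not require uncorrected sandwich standard errors. If one is wanted at step 4, name its small-sample correction and df method.

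Apply the same ladder to the secondary MMRMs, with two notes. PDQ-8 has only Weeks 8 and 12 (SAP 6.5), so it needs FA0(2). With two visits AR(1) and CS coincide, and their heterogeneous forms have 2 + 1 = 3 parameters, the same as unstructured. CGI-C is also assigned an ANCOVA in SAP 9.3, to which the ladder does not apply.

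The cost is a few more covariance parameters if a fallback is used, and slightly more SAP text and code. The change should be made before results are seen.
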